3.4 Concomitant Treatments

All medications taken within 28 days before the administration of study drug and all concomitant therapy administered during the study will be recorded on the relevant CRF, along with the reasons for and details of therapy use.

3.4.1 *Prohibited and/or Restricted Treatments*

- 1) Concurrent chemotherapy, hormonal therapy, immunotherapy regimens, or radiation therapy, standard or investigational. Exceptions include:
 - a) Palliative or supportive care may be offered to all subjects.
 - b) Palliative/therapeutic therapies (e.g., focal radiotherapy for pain or bone metastases, thoracocentesis or paracentesis for comfort) may be administered after consultation with the Medical Monitor.
 - c) Palliative radiation therapy for bone metastases is permitted, but subjects should not receive study treatment during radiation and must meet re-treatment criteria prior to resuming treatment.
 - d) Treatment of isolated symptomatic lesions by local surgery is permitted for palliative or potentially curative management at any time. All interventions should be discussed in advance with the BMS Medical Monitor. All tumor tissue that is not required for clinical pathology will be sent to BMS.
 - e) A new biopsy will not be required for resuming re-treatment in the setting of interrupted active treatment for local palliative therapies, although it is encouraged, if considered safe by the investigator. All tumor tissue that is not required for clinical pathology will be sent to BMS.
- 2) Use of growth factors including, but not limited to, granulocyte colony stimulating factor (G-CSF), granulocyte macrophage colony stimulating factor (GM-CSF), or erythropoietin stimulating agents are not permitted, unless deemed necessary by investigator and discussed with medical monitor.
- 3) Use of systemic corticosteroids at > 10 mg daily prednisone equivalent, unless required for the treatment of infusion reactions, other adverse events, or for palliation as determined by the investigator.
- 4) Use of RANKL therapy unless required for management of osteolytic bone lesions, other adverse events or for palliation and after a discussion between the investigator and the medical monitor. Since RANKL therapy is a recognized immune modulator, **discussion must occur before starting any patient on RANKL therapy.**

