8.3.2.2 Efficacy

The secondary objective relating to efficacy is to describe the anti-tumor activity of nivolumab and nivolumab in combination with ipilimumab in subjects with advanced melanoma. This objective will be measured by the following endpoints based on RECIST 1.1 criteria ([Appendix 2](#)). Disease evaluation will be performed at baseline, and then approximately every 8 weeks until disease progression or treatment discontinuation, whichever happens later.

The best overall response (BOR), computed for all treated subjects, is defined as the best response designation over the study as a whole, recorded between the dates of first dose until the last tumor assessment prior to subsequent therapy. CR or PR determinations included in the BOR assessment must be confirmed by a second scan performed no less than 4 weeks after the criteria

for response are first met. For those subjects who have surgical resection, only pre-surgical tumor assessments will be considered in the determination of BOR.

The objective response rate (ORR) is defined as the proportion of subjects with a BOR of CR or PR divided by the number of treated subjects (or response-evaluable subjects).

The Progression Free Survival Rate (PFSR) is defined as the probability of a subject remaining progression free or survival to time t , where $t=24$ weeks. This probability will be calculated by the product limit method (Kaplan-Meier estimates) which takes into account censored data.

The duration of response, computed for all treated subjects with a BOR of CR or PR, is defined as the time between the date of first response and the date of disease progression or death, whichever occurs first. For those subjects who remain alive and have not progressed or received subsequent therapy, duration of response will be censored on the date of last tumor assessment. For subjects who receive subsequent therapy prior to documented progression, duration of response will be censored on the date of subsequent therapy.

Progression free survival (PFS), computed for all treated subjects, is defined as the time between date of first dose of study therapy and date of progression or death, whichever occurs first.

[REDACTED]

[REDACTED]

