 - The minimum criteria for SD duration (6 weeks) must have been satisfied (considering the \pm 1 week tumor assessment window, 35 days will be used to derive SD).
- **Median Duration of Response (mDOR):** The significance of ORR is assessed by its magnitude and duration of response.
 - Duration of Response: DOR will be calculated for subjects with BOR of CR or PR only, and is defined as time between the date of first documented objective response and the date of the first subsequent disease progression or death, whichever occurs first, if death occurred within 100 days after last dose of study medication.
 - ◆ Subjects whose death occurred more than 100 days after last dose without prior progression will be censored at the last tumor assessment date (prior to subsequent therapy).
 - ◆ Subjects who remain alive and have not progressed will be censored on the last tumor assessment date (prior to subsequent cancer therapy).

- ◆ Subjects who receive subsequent therapy prior to documented disease progression, DOR will be censored on the date of last tumor assessment prior to subsequent therapy.
- **Median Time to Response (mTTR):** The objective response will be further characterized by the time to response.
 - Time to Response (TTR): The TTR for a subject with a BOR of CR or PR is defined as the time from the first dosing date to the date of the first documented objective response (CR or PR).
 - ◆ TTR will only be evaluated in subjects with a BOR of CR or PR.
- **Progression Free Survival Rate (PFSR) at Week t:** The proportion of subjects remaining progression free and surviving to time t, where t is a specific length of time, eg, 24 weeks, which will be determined by the available data for each interim or final analysis and will be documented in the data presentation plan (DPP). The proportion will be calculated by the product-limit method (Kaplan-Meier estimate) which takes into account censored data.
 - Progression Free Survival (PFS): The PFS for a subject is defined as the time from the date of first dose of study medication to the date of the first documented disease progression, or death due to any cause, whichever occurs first, if death occurred within 100 days after last dose of study medication.
 - ◆ Subjects who die within 100 days after last dose without a reported prior progression will be considered to have progressed on the date of their death.

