 - ◆ Subjects whose death occurred more than 100 days after last dose of study medication without prior progression will be censored at the last tumor assessment date (prior to subsequent therapy).
 - ◆ Subjects who remain alive and have not progressed will be censored on the last tumor assessment date (prior to subsequent cancer therapy).
 - ◆ Subjects who did not have any on study tumor assessment and did not die within 100 days after last dose of study medication will be censored on the date of first dose of study medication.
 - ◆ Clinical deterioration in the absence of radiographic evidence is not considered progression for the purpose of determining PFS when using objectively documented progression.
- **Overall Survival Rate (OSR) at Month t:** The proportion of subjects surviving to time t, where t is a specific length of time, eg, 12 months, which will be determined by the available data for each interim or final analysis and will be documented in the DPP. The proportion will be calculated by the product-limit method (Kaplan-Meier estimate) which takes into account censored data.
 - Overall Survival (OS): The OS for a subject is defined as the time from the date of first dose of study medication to the date of death for any cause.
 - ◆ A subject who has not died will be censored at last known date alive.

Note: For the final CSR, investigator assessed BOR, response date and progression date (as recorded on corresponding case report form [CRF]) will be used to derive efficacy endpoints.

For administrative interim analysis (or analyses), BMS internal derived BOR, response date and progression date will be used to derive efficacy endpoints (investigator assessed BOR, response date and progression date are usually missing at the time of interim analyses).

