 - In the event that this occurs, this will be treated as subject's subsequent therapy for certain efficacy assessments described in [Section 4.2.2](#).
- Subjects receiving treatment that is different than what they were assigned or randomized

- In the event that this occurs, subjects will be grouped with the actual received treatment (instead of assigned or randomized treatment) for the analyses.
- For Part 2, subjects whose on-treatment biopsy day relative to the start of study therapy is considerably different than the biopsy window which they were assigned.
 - In the event that this occurs, subjects would be grouped with their actual biopsy window (instead of assigned), or they would be excluded from the grouping schemes comparing the biopsy windows if their on-treatment biopsy is outside the 2 allowable windows.
- During the first dosing visit, if subjects receive ipilimumab dose first, before receiving the nivolumab dose during a visit which a combination therapy is planned.
- Subjects receiving immunosuppressive agents during the course of treatment on or prior to Cycle 2 Day 1 for Part 1 subjects and Week 13 Day 1 for Part 2-4 subjects.
 - In the event that this occurs, pharmacodynamic biomarker analyses may be repeated, as a sensitivity analysis, without these subjects or excluding data points after initiation of immunosuppressive agents.

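### Read literally, the SAP's PFS rules censor at subsequent therapy only those subjects who have no later event, so censoring depends on the outcome and PFS does not match DOR or BOR

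*SAP*

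**What the plan says.** SAP 4.2.2 gives this definition of PFS: "time from the date of first dose of study medication to the date of the first documented disease progression, or death due to any cause". Deaths count only within 100 days of last dose. Four parts of the plan then bear on subsequent therapy.

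- **PFS, no event.** "Subjects who remain alive and have not progressed will be censored on the last tumor assessment date (prior to subsequent cancer therapy". The late-death bullet, which likewise goes back to the scan before any new therapy, begins: "Subjects whose death occurred more than 100 days after last dose of study medication without prior progression will be censored at the last tumor".
- **PFS, early death.** "Subjects who die within 100 days after last dose without a reported prior progression will be considered to have progressed". The event is dated to the death, and no exception is made for therapy given in between.
- **DOR.** The DOR list contains corresponding bullets for subjects without an event and then adds one more: "Subjects who receive subsequent therapy prior to documented disease progression, DOR will be censored on the date of last tumor assessment prior to subsequent therapy". The PFS list has no counterpart. BOR also stops at subsequent therapy.
- **On-treatment therapy.** For anti-cancer therapy given before the last dose of study drug, SAP 7.2.3 says "this will be treated as subject's subsequent therapy for certain efficacy assessments", without naming the assessments.

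Protocol 8.3.2.2 gives PFS no rule for subsequent therapy. For DOR it uses a different date from the SAP: "For subjects who receive subsequent therapy prior to documented progression, duration of response will be censored on the date of subsequent therapy".

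**The concern.** Whether a subject leaves the PFS risk set at the scan before new therapy is decided by what happens after that therapy. A later progression keeps the subject at risk throughout and counts as an event. No later progression removes the subject retrospectively. After the start of therapy, only follow-up that ends in an event is used.

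The situation can arise in this study. Clinical deterioration without radiographic evidence is not a PFS event (SAP 4.2.2), so other therapy may begin before documented progression. Scans continue about every 8 weeks until confirmed progression or treatment discontinuation, whichever is later, and office follow-up then runs up to 100 days (SAP 6.1.3). A progression after the new therapy can therefore be recorded. In a responder, the same scan could be a PFS event while DOR has already been censored.

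The quantities affected are the PFS curve, its median, the 24-week PFS rate named in the Protocol, and PFS by PD-L1 level (SAP 7.8.2).

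**Working it through.** The documents state no PFS assumption or event count and no rate of subsequent therapy, so there is no planned figure to reproduce. Three rules are compared: (L) the literal text; (C) censor every subject at the last scan before subsequent therapy, as for DOR; (I) ignore subsequent therapy.

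**1. Direction of L against I.** The Kaplan-Meier estimate is the product over event times of (1 − d/n). L and I have the same events at the same times, so d is equal. L removes event-free subjects earlier, so n is never larger. Each factor is therefore no larger, and L can never lie above I.

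**2. A 40-subject example.** The size of 40 is that of a Part 1 cohort (SAP 2.1). Everything else is assumed. Six subjects progress at week 8, leaving 34, and 10 of those start other therapy after a clean week-8 scan. Of the 24 who do not, 6 progress at week 16, 6 at week 24 and 12 later or never. Six of the 10 never progress. The outcome of the other 4 varies by case.

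| 24-week PFS | L | C | I |
|---|---|---|---|
| Case 0: the 4 never progress | 34/40 × 18/24 × 12/18 = 42.5% | 42.5% | 22/40 = 55.0% |
| Case 1: the 4 progress at week 24 | 34/40 × 22/28 × 12/22 = 36.4% | 42.5% | 18/40 = 45.0% |
| Case 2: the 4 progress at week 48 | 34/40 × 22/28 × 16/22 = 48.6% | 42.5% | 22/40 = 55.0% |

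Under C, all 10 leave at week 8 in every case: 34/40 × 18/24 × 12/18 = 42.5%. Under I, all 34 stay at risk after week 8.

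Cases 0 and 2 have identical data up to week 24. Under L, four progressions at week 48 raise the 24-week rate from 42.5% to 48.6%. Neither C nor I changes. Case 2 also shows L above C, so the direction against C is not fixed.

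**3. Simulation.** There were 20 scenarios of 400,000 subjects each, with 8-week scans. Assumed inputs were a median PFS of 24 weeks; 10% to 38% starting other therapy before progression; a post-therapy hazard ratio of 1.0, 0.5 or 0.25; start of therapy unrelated or related to prognosis; and scans either continuing or stopping 16 weeks after therapy.

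- Against I, L was lower in all 20, by 0.2 to 6.1 points at week 24.
- Against C, L was lower in 16 of 20, including all 10 in which scans stopped. It was higher by 0.1 to 0.7 points in 4, where therapy slowed progression and scans continued.
- With 28% starting therapy, no therapy effect and scans stopping, L gave 46.4% at week 24 and 21.1% at week 48. Both C and I gave 50.0% and 25.0%.

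**4. When C itself is biased.** This run assumed a 6-month median, 16 weeks of later scans, and therapy five times as likely to start when progression would be seen at a scan within 8 weeks (13% affected). The true 24-week rate was 52.8%. L gave 51.4% and C gave 57.5%.

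**The case against.** The strongest reply is that no PFS bullet says progression after subsequent therapy counts. That reading comes from a general definition and a missing bullet. The parenthetical limits and the BOR cut-off suggest that a cut-off for everyone may have been intended. This stands as a point about intent. It does not rescue the text, because DOR has the same kind of parenthetical and still needed its own bullet.

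A reader might infer that reported PFS is simply biased low. The documents do not support that. It is certain only against ignoring therapy, and Case 2 reverses it against the DOR-type rule. Censoring deaths more than 100 days after last dose pushes PFS upward, so the net direction is not fixed.

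A reader might also infer that permitted palliative bone radiotherapy triggers the PFS rule. Protocol 3.4.1 says "Palliative radiation therapy for bone metastases is permitted, but subjects should not receive study treatment during radiation" and lists this as an exception to the prohibited treatments. SAP 7.2.3 names neither PFS nor this exception, so the link is unstated.

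It can also be said that the DOR-type rule is only one option, and that Protocol 8.3.2.2, which has no therapy cut-off for PFS, fits ignoring therapy at least as well. Step 4 shows that C can be further from the truth than L. That stands, and it is why both consistent analyses are needed.

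Finally, the shifts are small beside sampling error. Near 50%, the approximate 95% half-width is 1.96 × √(0.25/40) = 15.5 points for 40 subjects and 1.96 × √(0.25/10) = 31 points for 10. This limits the consequence but does not make the rule coherent.

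**Conclusion.** The point holds as a defect in the literal PFS rule. Censoring at subsequent therapy depends on the later outcome, which breaks the Kaplan-Meier assumption and makes PFS inconsistent with DOR and BOR in the same section. The direction is certain against ignoring therapy, and usual but not guaranteed against censoring everyone. The percentages above rest on assumed shares, timing and therapy effects, so they show what is possible and do not estimate what will happen in this trial. PFS is secondary and descriptive, and the SAP plans no formal inference needing adjustment of the significance level. No error rate or sample size changes. The correction should be made before the final analysis, but it does not threaten the primary objective.

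**What to change.** 1. Add a PFS bullet to SAP 4.2.2 mirroring the DOR one: anyone who starts other anti-cancer therapy with no progression yet documented is censored at the last scan before it, regardless of what is seen later.
2. State whether this bullet also applies to deaths within 100 days of last dose, and to the on-treatment therapy of SAP 7.2.3, including palliative radiotherapy that the Protocol permits.
3. Use one censoring date for PFS and DOR, and reconcile Protocol 8.3.2.2 (date of the therapy) with the SAP (last assessment before it).
4. Add a sensitivity analysis that ignores subsequent therapy for all subjects, counting later events and later follow-up alike.

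The cost is a few sentences and one more Kaplan-Meier run. The main analysis will have slightly fewer PFS events. Censoring at therapy may also be informative, biasing PFS upward, if therapy starts because a subject is deteriorating. Item 4 is there to show whether that matters.

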4.2.2 Preliminary Anti-tumor Activity

The secondary objective relating to efficacy is to describe the anti-tumor activity of nivolumab and nivolumab in combination with ipilimumab in subjects with advanced melanoma. Changes in tumor measurements and tumor response will be measured based on RECIST 1.1. Disease evaluation will be performed at baseline, and then prior to each cycle for Part 1, or prior to the

[figure not shown]
first dose of the next treatment visit for Parts 2-4, approximately every 8 weeks until confirmed disease progression or treatment discontinuation, whichever happens later. Patients will be followed for overall survival up to 2 years from the first dose of study medication or for those patients that enter the Extension Period, overall survival assessments will be continued for 100 days following the last treatment dose. The following set of efficacy study-level endpoints will be used:

[figure not shown]
- **Objective Response Rate (ORR):** The total number of subjects whose best overall response (BOR) is either a complete response (CR) or partial response (PR) divided by the total number of subjects in the population of interest (eg, all treated subjects or response-evaluable subjects).
 - Best Overall Response: The subject's best response designation over the study as a whole, recorded between the date of first study drug administration and the date of objectively documented progression per RECIST 1.1, with subsequent confirmation, or date of subsequent anti-cancer therapy, whichever occurs first in the study.
 - ◆ For those subjects who have surgical resection, only pre-surgical tumor assessments will be considered in the determination of BOR.
 - ◆ For subjects without documented progression per RECIST 1.1 or subsequent anti-cancer therapy, all available response designations will contribute to the BOR determination.
 - ◆ For subjects who continue treatment beyond progression, the BOR should be determined based on response designations recorded up to the time of the initial RECIST 1.1 defined progression.
 - ◆ For a BOR of CR or PR, the response assessment must have been confirmed by a consecutive assessment meeting the criteria for response and performed no less than 4 weeks (28 days) after the criteria for response are first met.
 - ◆ For a BOR of stable disease (SD), the following criteria will be applied to the SD derivation:

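### The final CSR takes best overall response and its dates from the CRF, with no rule that they respect the SAP's cut at initial progression or which value prevails

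*SAP*

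**What the plan says.** SAP 4.2.2 sets subject-level rules for BOR. On treatment past progression it says: "For subjects who continue treatment beyond progression, the BOR should be determined based on response designations recorded up to the time of the initial RECIST" 1.1-defined progression. A CR or PR needs a consecutive confirming assessment, "performed no less than 4 weeks (28 days) after the criteria for response are first met". Stable disease needs 35 days, and only pre-surgical scans count. For PFS: "Clinical deterioration in the absence of radiographic evidence is not considered progression for the purpose of determining PFS", a sentence that goes on to limit itself to analyses using objectively documented progression.

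The Note closing the section then names the data source. For the final report: "For the final CSR, investigator assessed BOR, response date and progression date (as recorded on corresponding case report form [CRF]) will be used". For interims: "For administrative interim analysis (or analyses), BMS internal derived BOR, response date and progression date will be used to derive efficacy endpoints". The reason given is that "investigator assessed BOR, response date and progression date are usually missing at the time of interim analyses".

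The protocol's BOR window is different. In Protocol 8.3.2.2, BOR "is defined as the best response designation over the study as a whole, recorded between the dates of first dose until the last tumor assessment" before subsequent therapy, with no stop at progression. Appendix 2 (section 4.2) runs it to the end of treatment. Protocol 4.3.8 allows treatment beyond initial progression and dates investigator-assessed progression at the initial event.

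**The concern.** The SAP writes one definition of response and then feeds the final analysis with a summary value that investigators complete under another document. An investigator who follows the protocol exactly can record a BOR that SAP 4.2.2 would exclude. The visible text has no check of CRF values against Section 4.2.2, no order of precedence, and no final analysis using the sponsor-derived values.

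At stake are the final ORR, time to response, duration of response (DOR) and the response-by-PD-L1 tables. Interim results may support publications and program decisions, so a figure already presented could change in the CSR with no new scan behind it, only a change of source. PFS is less exposed. Its open question is whether a CRF progression date may rest on clinical judgement alone.

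**Working it through.** The plan states no figure to reproduce. The check compares the rules on one record, tests which rules can actually diverge, and sizes one reclassification.

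**1. One record under both sets of rules.** Parts 2–4 scans (Protocol Tables 5.1D and 5.1E) fall at weeks 7, 13 and 23, then every 8 weeks. With day = 7 × (week − 1) + 1, weeks 7, 13, 23 and 31 are days 43, 85, 155 and 211. Take SD at week 7, PD at week 13 with treatment continued, then PR at weeks 23 and 31. This is possible because Appendix 2 measures PR against the baseline sum.

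| Item | SAP 4.2.2 rules | CRF completed under the protocol |
|---|---|---|
| BOR window | ends at week 13 | continues past week 13 |
| Confirmation | not reached | 211 − 155 = 56 days, at least 28 |
| BOR | SD | PR |
| Response date | none | week 23 (day 155) |
| Progression date | week 13 (day 85) | week 13 (Protocol 4.3.8) |
| In the DOR analysis | no | yes |

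The SAP ends DOR at the first progression after the response, or at death within 100 days of the last dose. The recorded progression comes before the response, so it cannot be that end. The censoring branch for subjects who have not progressed does not fit either, because this subject has a progression date. Nothing visible tells the programmer what to do.

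**2. Interim against final.** At an interim the sponsor derives BOR. Under the Section 4.2.2 rules this subject is SD; at the final analysis the CRF entry can make the same subject a responder.

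**3. Which other rules can diverge.**
- *Confirmation.* Protocol 8.3.2.2 also requires at least 4 weeks. Appendix 2 (4.1.2) instead asks for confirmation inside 4 weeks. Scheduled scans, which may be up to 7 days early, are at least 85 − 7 − 43 = 35 days apart in Parts 2–4. In Part 1 the gap is at least 56 − 14 = 42 days. Only an unscheduled scan before day 28 would satisfy Appendix 2 and fail the SAP.
- *SD duration.* The earliest nominal first scan in Parts 2–4 is day 43 − 7 = 36, which meets 35 days. The ±2-day visit window could bring it to day 34, a marginal exception.
- *Surgery.* The pre-surgical limit is in Protocol 8.3.2.2 as well.
- *Progression date.* Protocol 4.3.8 holds it at the initial event. The documents do not say whether a CRF date can be clinical only, although both list clinical progression in the response-evaluable definition.

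**4. Size per reclassified subject.** The ORR shift is 1/n, and only for a change between responder and non-responder.
- Cohort 1, Cohort 2, or Arm A pooled over Parts 2 and 3 (20 + 20 = 40): 1/40 = 2.5 points.
- Arm A within Part 2 or Part 3: 1/20 = 5 points.
- Arms B, D or E: 1/10 = 10 points.
- Cohort 1 combined with Arm B, as Protocol 8.4.2 plans for efficacy: 1/50 = 2 points.

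For scale, assume an ORR of 30% on the CRF and one responder removed; intervals are 95% Clopper–Pearson. At n=10, 3/10 (6.7% to 65.2%) becomes 2/10 (2.5% to 55.6%). At n=40, 12/40 (16.6% to 46.5%) becomes 11/40 (14.6% to 43.9%).

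**The case against.** The strongest defence is that the Note names a source for three inputs and waives nothing. A reader might infer that the final analysis bypasses the SAP's rules; the documents do not say that. The DOR and PFS censoring rules still apply to whatever dates are supplied, and SAP 7.8.2 requires confirmed CR or PR for the CSR. Investigator assessment is a legitimate source for descriptive secondary endpoints with no formal inference. The interim/final difference is disclosed and explained. Lesion and visit-level data will be listed, and the CRF guidelines and Data Presentation Plan, which were not available, may contain a check.

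Four stronger readings also fail:
- *A DOR of −70 days* (85 − 155). The SAP counts only progression after response, so the result is an undefined end date, not a negative duration.
- *Unconfirmed responses entering the final ORR.* Protocol 8.3.2.2 forbids this, so it would be an investigator error, not a gap between the documents.
- *Clinical deterioration certainly handled differently.* The SAP rule is conditional and the CRF content is unknown.
- *Any discordance rate translating directly into ORR points.* That needs every discordance to cross the responder boundary in one direction. SD/PD disagreements move ORR by zero.

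What survives is that both documents, followed as written, still allow a post-progression response to be the CRF BOR, and no visible rule resolves the conflict.

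**Conclusion.** The point holds as a missing reconciliation rule between the CRF values and SAP 4.2.2. The main exposure is responses recorded after initial progression, with a secondary question about clinical-only progression dates. The confirmation, SD-duration and surgery rules are largely protected by the protocol and the scan schedule.

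The effect is 2.5, 5 or 10 ORR points per subject reclassified across the responder boundary at n=40, 20 or 10, plus a DOR with no defined end for each such subject. How many there would be is unknown. The n=30 for Arm A in the sample-size section counts biopsies in the optimal window and is not the ORR denominator.

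This should be corrected, but it does not touch the primary biomarker objective or any error rate. The conclusion assumes that investigators complete BOR as the protocol defines it and that no check sits in documents not seen.

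**What to change.** Replace the Note with a rule that, for the final CSR as for interims, BOR, response date and progression date are derived by program from the investigator's time-point tumor assessments under Section 4.2.2. The investigator remains the assessor. State whether progression recorded on clinical grounds alone counts for PFS and DOR. List the CRF-recorded BOR and dates beside the derived ones, with a concordance table and ORR by CRF BOR as a sensitivity analysis. Align the confirmation interval in Appendix 2 with Protocol 8.3.2.2 and SAP 4.2.2.

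The cost is a short SAP edit, the Appendix 2 alignment and one extra table. A derivation is already planned for interims, and the lesion and visit data are already collected. The reported ORR may be slightly lower, because post-progression responses would no longer count in the main analysis.
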